9.1.1. Endpoints

Primary Endpoints:

- a. Response based on achieving the **IGA** of clear (0) or almost clear (1) (on a 5-point scale) at month 3.
- b. Response based on achieving the **EASI-75** at month 3.

Secondary Endpoints:

Physician's global assessment of efficacy parameters (assessed at all visits [except for month 3 for a. and b.]):

- a. Response based on achieving the **IGA** of clear (0) or almost clear (1) (on a 5-point scale).
- b. Percentage of patients with EASI-75 response compared to baseline.
- c. Response based on achieving the EASI-90.
- d. Response based on achieving the **IGA** of clear (0) or almost clear (1) and a reduction from baseline of ≥ 2 points.
- e. Percentage change of **IGA** compared to baseline.
- f. Percentage change of **SCORAD** compared to baseline.
- g. Absolute **EASI** values over time.
- h. Percentage change of EASI compared to baseline.
- i. Absolute change of **IGA** compared to baseline.

Patient's assessment of efficacy and quality parameters (assessed at all visits):

- a. Response based on achieving at least 4 points improvement of Pruritus **NRS** from baseline.
- b. Change of Peak-Pruritus NRS over time.
- c. Change of **POEM** from baseline.
- d. Change of MOS from baseline.
- e. Change of DLQI from baseline.

- f. Change of HADS from baseline.
- g. Change of EuroQol five-dimensional-five level (EQ-5D-5L) from baseline.
- h. Patient's satisfaction with treatment measured by PBI.
- i. Patient's expectation of treatment measured as PBI at baseline.
- j. Number of days with topical-treatment use (TCS, TCI).
- k. Number of days with emollients use.

Explorative Endpoints:

Treatment characteristics (assessed at all visits):

- a. Concomitant treatments.
- b. Tolerability of abrocitinib and reasons for discontinuation.
- c. Dosage of abrocitinib.
- d. Compliance with abrocitinib treatment.

Patient characteristics assessed at baseline visit only (except for c., f., g., and h. with additional assessment at subsequent visits):

- a. Demographic data of patient (age, sex, weight, occupation, alcohol/smoking, family history).
- b. Clinical history of AD treatment before non-interventional study start.

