DLQI	Secondary outcome variable	Case records	 Percentage of patients achieving at least 4 points improvement of DLQI from baseline Summary statistics (n, mean, median, standard deviation, minimum and maximum) of the score at each point in time as well as the percentage change to baseline Percentage of patients with DLQI ≤1
POEM	Secondary outcome variable	Case records	Summary statistics (n, mean, median, standard deviation, minimum and maximum) of the score at each point in time as well as the percentage change to baseline
MOS-Sleep scale	Secondary outcome variable	Case records	Summary statistics (n, mean, median, standard deviation, minimum and maximum) of the

scales at each point in time as well as the percentage change to baseline Summary statistics (n, mean, median, standard deviation, minimum and maximum) of the Patient single items and the total score at Case records Benefit Secondary outcome variable each appropriate point in time as Index well as the percentage change to visit 2 (about one months after baseline) Patient Expectation As measured by PBI questionaire s on and (refer to line above; expectation Satisfaction PBI at baseline, satisfaction PBI at Secondary outcome variable Case records with all points in time after baseline) abrocitinib treatment Summary statistics (n, mean, median, standard deviation. minimum and maximum) of the EQ-5D-5L VAS and EQ-5D index score at Secondary outcome variable Case records each point in time as well as the percentage change to baseline Summary statistics (n, mean, median, standard deviation, minimum and maximum) of the **HADS** anxiety score and depression score Secondary outcome variable Case records at each point in time, respectively as well as the percentage change to baseline Number of Date of first topical treatment – date days with of last topical treatment + 1 topical treatment Secondary outcome variable Case records Summary statistics (n. mean. median, standard deviation, use (TCS, TCI) minimum and maximum) Date of first emollients use – date of last emollients use + 1 Number of days with emollients Secondary outcome variable Case records Summary statistics (n, mean, use median, standard deviation, minimum and maximum)

Analysis of questionnaires

Questionnaire	Analysis
SCORAD	Scoring Atopic dermatitis: validated scoring index for AD for severity, combining A: extent (0-100), B: severity (0-18) and C: subjective symptoms (0-20) based on itching and sleep deprivation,

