	question, 0 to 3 points are given, whereby 3 points indicate the greatest possible impairment of the QoL in the queried area. The sum of scores ranges from 0 to 30, with higher scores indicating greater impairment of quality of life. If one question is unanswered it is scored with 0. If more than one question is not answered the score cannot be determined.
	(https://www.cardiff.ac.uk/medicine/resources/quality-of-life-questionnaires/dermatology-life-quality-index)
MOS	The Medical Outcomes Study Sleep Scale (MOS-Sleep) includes 12 items assessing sleep disturbance (questions 1, 3 (R-reversed), 7 (R) and 8(R)), sleep adequacy (questions 4 (R) and 12 (R)), somnolence (questions 6 (R), 9(R) and 11 (R)), quantity of sleep (question 2), snoring (question 10 (R)), and awakening short of breath or with a headache (question 5 (R)) whereat question 1 scores from 1 (0-15 min) to 5 (>60 min) and questions 3 to 12 from 1 (all of the time) to
	5 (none of the time). 1 is recoded to 0, 2 to 25, 3 to 50, 4 to 75 and 5 to 100. If the answers have to be reversed 1 is recoded to 100, 2 to 75, 3 to 50, 4 to 25 and 5 to 0. The scores represent the average for all items in the scale that were answered, i.e. missing data are not taken into account.
PBI	Measurement of patient defined treatment benefits according to German and international standards, contains two one-sided questionnaires which are to be completed by the patient before and after receiving a treatment. A total of 25 possible treatment goals are evaluated on an
	importance scale from 0 ("not at all") to 5 ("very"). "does not apply to me" will be coded as "0". The analysis will include: a) means and standard deviations of all items ("does not apply to me" is
	coded as 0 for this single-item analysis of the PBI) b) for each item the percentage of the response "does not apply to me" c) for each item the percentage of responses with high agreement (quite or very) d) percentage of missing values The weighted index value, the actual "Patient Benefit Index"
	(PBI), is calculated by multiplying the achieved benefits (respective PBI after baseline) with the importance of the respective needs prior to therapy (PBI at baseline), dividing these products by the sum of all importance items (PBI at baseline), and summing them up for all items. The total PBI score ranges from 0 (no benefit) to 5 (maximal benefit).

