Outcome **Analysis Set Supports Missing Data** Subgroups Statistical Method Covariates/ Strata Protocol **Objective** Number baseline)/score at baseline*100 Mann-Whitney-U test for subgroups Change of EuroQol five-(score at respective FAS, mFAS, PP All None Excluded dimensional-five level visit - score at (EQ-5D-5L) from baseline)/score at 21 baseline baseline*100 Mann-Whitney-U test for subgroups Change of PBI from FAS, mFAS, PP All (score at respective None Excluded visit - score at baseline baseline)/score at 22 baseline*100 Mann-Whitney-U test for subgroups Patient's satisfaction FAS, mFAS, PP All Frequency tables for None Excluded satisfaction with with treatment (PBI after baseline) effectiveness and tolerability 23 Chi-Square test respective Fisher's exact test for subgroups Number of days with FAS, mFAS, PP All Excluded Summary statistics (n, None topical-treatment use mean, median, standard deviation, (TCS, TCI) 24 minimum and maximum) Mann-Whitney-U test for subgroups Number of days with FAS, mFAS, PP All Summary statistics (n, None Excluded emollients use mean, median, standard deviation, 25 minimum and maximum)

Outcome	Analysis Set	Supports Protocol Objective Number	Subgroups	Statistical Method	Covariates/ Strata	Missing Data
				Mann-Whitney-U test for subgroups		
AD-treatment with abrocitinib and/or without topicals – total days	FAS, mFAS, PP	26	All	Summary statistics (n, mean, median, standard deviation, minimum and maximum) Mann-Whitney-U test for subgroups	None	Excluded
AD-treatment with abrocitinib and/or without topicals – stratified by abrocitinib dose	FAS, mFAS, PP	27	All	Summary statistics (n, mean, median, standard deviation, minimum and maximum) Mann-Whitney-U test for subgroups	None	Excluded
Number of flares	FAS, mFAS, PP	28	All	Summary statistics (n, mean, median, standard deviation, minimum and maximum) Mann-Whitney-U test for subgroups	None	Excluded

All explorative endpoints mentioned in section 6.3 will be analyzed for FAS and all subgroups, respectively. Safety enpoints, as given in section 6.2 will be analyzed for SAF.

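### Two PBI rows in SAP 8.2.3 contradict SAP 6.1: one takes change from a baseline index that does not exist, the other tabulates satisfaction categories with no defined source variable

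*SAP*

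**What the plan says.** Protocol 9.1.1 lists two secondary endpoints based on the PBI: "Patient's satisfaction with treatment measured by PBI" and "Patient's expectation of treatment measured as PBI at baseline". Protocol Section 8 and SAP 1.3 give the matching secondary objective, which is whether patients' expectations are met, expressed as change in the PBI.

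SAP 6.1 makes these operational. (In the SAP quotes that come from tables, text from neighbouring columns can run together.)

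- The PBI line asks for summary statistics of single items and total score, as "well as the percentage change to visit 2 (about one months after baseline").
- The expectation and satisfaction line refers back to it: "As measured by PBI questionaire s on and (refer to line above; expectation Satisfaction PBI at baseline, satisfaction PBI at Secondary outcome variable" all later time points.
- The questionnaire table describes the instrument: "A total of 25 possible treatment goals are evaluated on an" importance scale from 0 to 5. It then defines the outputs and the weighted index, which runs from 0 (no benefit) to 5 (maximal benefit).

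SAP 8.2.3 has two PBI rows, identified here by the number in its objective column.

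- Row 22: "Change of PBI from FAS, mFAS, PP All (score at respective None Excluded". The method is visit score minus baseline score, divided by baseline score, times 100, with a Mann-Whitney-U test for subgroups.
- Row 23: "Patient's satisfaction FAS, mFAS, PP All Frequency tables for None Excluded satisfaction with", continuing "with treatment (PBI after baseline) effectiveness and tolerability 23 Chi-Square test respective Fisher's exact test for subgroups".

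**The concern.** A programmer who works from 8.2.3 meets two instructions that the rest of the SAP does not support.

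Row 22 needs a baseline value of an index that can only be calculated after baseline. The numbers available at baseline are importance ratings, which are a different quantity from benefit achieved. Using them as the denominator gives a ratio of two constructs.

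Row 23 needs patient ratings of satisfaction with effectiveness and with tolerability, under a label that says the outcome is the PBI. Someone would have to look for a variable the documents do not define, or choose a substitute at the time of analysis without a record of the choice.

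This matters beyond tidiness because SAP Section 4 takes the hypothesis-generating subgroup tests from 8.2.3, and because row 22 is the summary row for a stated secondary objective.

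**Working it through.** The plan gives no figure to reproduce, so the check sets the sections side by side.

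**Row 22**

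1. Write w_i for the importance of goal i at baseline and b_i for the benefit on goal i at a later visit. The formula in SAP 6.1 is PBI = sum(b_i × w_i) / sum(w_i).
2. At baseline the w_i exist and the b_i do not, so the index is undefined there. The first visit at which it can be calculated is Visit 2.
3. The PBI line of 6.1 is consistent with this, since it uses Visit 2 as reference. Row 22 uses baseline. The two cannot both be followed.
4. As an illustration only, suppose mean importance were put in as the baseline score. All values here are assumed; neither document gives any. With a later index of 3 out of 5:
   - mean importance 2: (3 − 2)/2 × 100 = +50%
   - mean importance 3: (3 − 3)/3 × 100 = 0%
   - mean importance 4: (3 − 4)/4 × 100 = −25%
   - mean importance 5: (3 − 5)/5 × 100 = −40%

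   The same benefit prints as a gain or a loss depending on how much the patient wanted at the start.

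**Row 23**

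1. The PBI outputs in SAP 6.1 are item means and SDs, the per-item share answering that the goal does not apply, the per-item share with high agreement, the share missing, and the weighted index. None is defined as satisfaction with effectiveness or with tolerability.
2. Other possible sources:
   - The schedules (Protocol Table 1, SAP Table 1) contain the PBI at every visit and no separate satisfaction item.
   - Protocol Table 2 lists the PBI, and a tolerability/safety variable whose roles include safety outcome. It lists no patient satisfaction rating.
   - Protocol 9.2.4.7 says satisfaction is asked of the patient at Visits 2 to 6, but names no instrument and no such split.
   - Protocol 9.2.4.10 has a general tolerability rating, made by the healthcare professional.
3. For the same endpoint, 6.1 calls for summary statistics of PBI items and total score. Row 23 calls for frequency tables of something else.

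**Reach**

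SAP 8.2.2 refers to the operational definitions in 6.1, so the main PBI summaries can be run from there. SAP Section 4 takes the subgroup tests from 8.2.3, so those tests do depend on the two rows.

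**The case against.** The strongest reply is that 8.2.3 is only a summary. SAP 8.2.2 sends the analyst to 6.1, and 6.1 has a complete PBI analysis. That stands. A reader might infer that the satisfaction endpoint has no executable analysis; the documents do not support that.

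A reader might also infer that the PBI does not cover effectiveness or tolerability at all. Neither document lists the PBI items, so that cannot be shown. What can be shown is that the scoring in 6.1 defines no such output. The table shells are in a separate file and could not be checked.

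Nor is it right that there is no PBI at baseline. Both documents use that name for the baseline importance questionnaire. It is the weighted index that is missing there.

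The row lists three analysis sets, but under SAP 5.3 the mFAS is used only if at least 10% of the FAS is omitted, and the PP set only if at least 10% of the mFAS is omitted. Three sets of outputs are therefore not certain.

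Finally, Protocol Section 5 reports that an unvalidated standalone question on expectation and satisfaction was removed and the PBI kept. Row 23 may be a remnant of that question. This is an inference, since the documents do not say what the question asked.

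None of this removes the conflict between 6.1 and 8.2.3 in the current text.

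**Conclusion.** The point holds as a contradiction within the SAP. Row 22 as written has no defined baseline value to divide by. Row 23 as written has no defined source variable. Both are wrong analysis rules rather than missing detail, because 6.1 already gives a different rule for the same outcomes.

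The size is modest. Two rows of 8.2.3 and their subgroup tests are affected, all for descriptive secondary endpoints in a study without formal hypotheses. The illustrative percentages show the direction of the problem under one possible misreading. They are not a predicted result, and the SAP nowhere instructs the analyst to divide by mean importance.

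The conclusion rests on the PBI description and scoring in SAP 6.1 and Protocol 9.2.4.9, and on the absence of any other satisfaction variable in the schedules and variable list.

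**What to change.** **Row 22.** Replace change from baseline with change from Visit 2, as in 6.1, reported at Visits 3 to 6. State how a Visit 2 index of 0 is handled, since the percentage is then undefined. Do not delete the row, because change in PBI is a stated secondary objective.

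**Row 23.** Replace the method with outputs already defined in 6.1, at Visits 2 to 6:

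- summary statistics of the weighted 0 to 5 index, with Mann-Whitney-U for subgroups;
- per-item percentages with high agreement, with Chi-Square or Fisher's exact test for subgroups.

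If separate items on satisfaction with effectiveness and tolerability are still collected, name the source variable and do not label it PBI.

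In the same edit, reconcile the number of treatment goals, given as 23 in Protocol 9.2.4.9 and 25 in SAP 6.1.

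The cost is SAP wording and two table shells. No new data are needed.

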4 HYPOTHESES AND DECISION RULES

As the protocol states, this is a solely descriptive and explorative non-interventional study with the aim to generate hypothes. In order to generate hypotheses the statistical tests mentioned in section 8.2.3 are carried out for the subgroups defined in section 5.4.

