5.4 SUBGROUPS

The following subgroups will be analysed:

- Sequence of dosage (50 mg → 100 mg vs. 100 mg → 50 mg vs. 100 mg → 200 mg vs. 200 mg → 100 mg vs. 200 mg vs. 50 mg)
- Medication history* (prior conventional systemic treatment, prior biologic, prior JAKi, none of those)
- Dosage switchers (patients who switched from abrocitinib vs. patients who remain on abrocitinib)
- Abrocitinib responder, defined as: EASI-75-responder and/or SCORAD-75-responder and/or IGA 0/1
- EASI-90 responder (yes vs. no)

If less than 20 patients are in one subgroup class, classes will be combined in a meaningful way or the subgroup analysis will be omitted with reason.

*Pfizer will assign the prior medication documented to (i) topical (TCS,TCI,other), (ii) systemic (conventional, biologics, JAKi, other), (iii) phototherapy and (iv) other in order to analyze the pretreatment and form the subgroup "medication history" accordingly.

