6.3 OTHER ENDPOINTS

Variable	Role	Data source(s)	Operational definition	
AD-treatment with abrocitinib and/or without topicals – total days	Exposure, Potential confounder, potential subgroup identifier	Case records	Date of last treatment – date of first treatment +1 Summary statistics (n, mean, median, standard deviation, minimum and maximum)	
AD-treatment with abrocitinib and/or without topicals – stratified by abrocitinib dose Exposure, Potential confounder, outcome, potential subgroup identifier		Case records	Date of last treatment – date of first treatment +1 Summary statistics (n, mean, median, standard deviation, minimum and maximum) stratified by the abrocitinib dose most often applied during the study	
Age (Year of birth)	Baseline characteristics, potential confounder, potential subgroup identifier	Case records	Age=year of IC – year of birth Summary statistics (n, mean, median, standard deviation, minimum and maximum)	
Sex	Baseline characteristics, potential confounder, potential subgroup identifier	Case records	Frequency analysis	
Height Baseline characteristics		Case records	Summary statistics (n, mean, median, standard deviation, minimum and maximum)	
Weight Baseline characteristics		Case records	Summary statistics (n, mean, median, standard deviation, minimum and maximum)	
Highest level of education	Baseline characteristics, potential confounder	Case records	Frequency analysis	
Ethnicity Baseline characteristics		Case records	Frequency analysis	

Occupational status	Baseline characteristics	Case records	Frequency analysis
Alcohol consumption status	Baseline characteristics, potential confounder	Case records	Frequency analysis
Insurance type	Baseline characteristics	Case records	Frequency analysis
Presence of family history of atopic diseases	Baseline characteristics, potential confounder, potential subgroup identifier	Case records	Frequency analysis
History of herpes simplex and/or eczema herpeticum and/or herpes zoster	Baseline characteristics	Case records	Frequency analysis
Vaccination status (Herpes zoster, Covid-19, Influenza Varicella)	Baseline characteristics	Case records	Frequency analysis
Age at initial diagnosis of AD	Baseline characteristics, potential confounder	Case records	Age at initial diagnosis =year of initial diagnosis – year of birth 1. Summary statistics (n, mean, median, standard deviation, minimum and maximum) 2. Categorical: < 12 y, 12-<18 y and ≥ 18 y

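### The planned tests of days on abrocitinib are circular for switched versus remained, and carry immortal time for changed versus constant dose

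*SAP*

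**What the plan says.** SAP 8.2.3 lists days on abrocitinib in row 26 ("AD-treatment with abrocitinib and/or without topicals – total days") and again by dose in row 27. Both rows specify a Mann-Whitney U test, enter All under Subgroups and enter None under Covariates/Strata. A closing sentence in 8.2.3 sends every explorative endpoint of section 6.3 to all subgroups as well.

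SAP 6.3 derives the outcome as "Date of last treatment – date of first treatment +1", with no event or censoring indicator. Row 27's version is "stratified by the abrocitinib dose most often applied during the study".

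SAP 5.4 gives five subgroups:

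- "Sequence of dosage", which as printed has four changed-dose and two constant-dose classes;
- medication history, in four classes ("prior conventional systemic treatment, prior biologic, prior JAKi, none of those");
- a split by whether the patient stays on the drug: "Dosage switchers (patients who switched from abrocitinib vs. patients who remain on abrocitinib");
- a split by clinical response: "Abrocitinib responder, defined as: EASI-75-responder and/or SCORAD-75-responder and/or IGA 0/1";
- a stricter response split, at a 90% reduction in EASI.

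Neither responder definition gives a time point, and SAP Appendix 1 adds none. Classes of fewer than 20 patients are combined or dropped.

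On purpose, SAP section 4 says: "In order to generate hypotheses the statistical tests mentioned in section 8.2.3 are carried out for the subgroups defined in section 5.4". SAP 8.1 makes no multiplicity adjustment, and no significance level is stated.

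**The concern.** A test between groups is informative only if group membership is not itself produced by the outcome. Here the five subgroups differ:

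- **Switched versus remained.** Patients who leave the drug have fewer days on it because they left. The label speaks of dosage while the definition speaks of leaving abrocitinib. The two should be reconciled.
- **Dose sequence.** A patient enters a changed-dose class only by still being on drug when the dose changes. Early stoppers collect in the constant-dose classes. The time before the change is immortal time.
- **Responder status.** Longer time on drug gives more chances to be classed as a responder, but only if response is documented mainly on treatment or patients are lost after stopping.
- **Medication history.** This is fixed at baseline and has no such problem.

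Usage of abrocitinib is a stated objective (SAP 1.3), and the rationale in SAP section 1 expects results that help optimise therapy. A table showing that patients with a dose change stayed on drug weeks longer, with a very small p-value, could be read as evidence that changing the dose prolongs persistence.

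**Working it through.** The documents give no error rate, persistence or dose-change figure for these tests, so there is no plan figure to reproduce. Inputs from the documents are N = 750, 12 months of observation (365 days), the outcome definition and the minimum class size of 20. **Assumed:** two-sided 5% level; 12-month persistence S = 50–80%; share due a dose change by month 12, q = 15–45%; exponential times; dose change independent of stopping; every stop counted as a switch.

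**1. Switched versus remained.** With complete follow-up every remainer has 365 days and every switcher fewer, so P(remainer has more days) = 1. Even at 20 versus 20, U = 400 against a null mean of 200 and a standard deviation of √(20·20·41/12) = 37.0, so z = 200/37.0 = 5.4 (larger after tie correction). Simulated at N = 750, with 5–50% discontinuation and 0–50% loss to follow-up, rejection is 99.7–100%. It was also 100% at a 0.1% level where checked. It weakens only near the minimum class size with heavy loss: 20 versus 20 gives 96% at 30% loss and 73% at 50%. Within row 27 dose strata of 60–300 patients (30% discontinuation) it is 99.8–100%.

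**2. Changed versus constant dose.** Let λ = −ln(S)/365, μ = −ln(1−q)/365, k = λ+μ, e = exp(−365k), and D = days on drug.

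- P(constant) = (λ/k)(1−e) + e
- E[D; constant] = λ[(1−e)/k² − 365e/k] + 365e
- E[D] = (1−S)/λ
- Mean if changed = (E[D] − E[D; constant]) / (1 − P(constant))

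For S = 0.65 and q = 0.30: e = 0.65 × 0.70 = 0.455; P(constant) = 0.547 × 0.545 + 0.455 = 0.753, so about 185 of 750 are changed.

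| S | q | Mean days, changed | Mean days, constant | Difference |
|---|---|---|---|---|
| 0.80 | 0.15 | 350.9 | 323.4 | 27.5 |
| 0.65 | 0.30 | 336.8 | 283.4 | 53.4 |
| 0.50 | 0.45 | 318.0 | 235.7 | 82.3 |

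No effect of dose change exists in this model, so the whole difference is artefact. Simulated rejection, pooled changed versus constant, is 81–100%. Splitting start doses 10/50/40% over 50/100/200 mg, with half of the 100 mg changers going up (assumed), individual changed-versus-constant sequences give about 22–100%. The bias in days stays the same; only power falls with class size. Changed versus changed (100→200 against 200→100 mg) gives about 2–6%, which is nominal.

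**3. Responder, ever versus never** (60% responding by month 12 assumed).

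- Response counted only on treatment: 100%.
- Counted at all visits, no loss: about 5%.
- Counted at all visits, 10–20% loss: 53–100%.

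**4. Controls under the same null.** A baseline-defined group such as medication history gives 3–8%. Dose change fixed at day 91, with only later time counted, gives 4–7% by Mann-Whitney and 3–7% by log-rank. The excess therefore comes from how the classes are formed.

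**5. Class size at a day-91 landmark.** The 100→200 mg class is 750 × 0.5 × 0.5 × [1 − (1−q)^(91/365)] × S^(91/365). This is 187.5 × 0.040 × 0.841 = 6 at the low end and 187.5 × 0.138 × 0.946 = 24–25 at the high end, often below 20. Pooling all changers (750 in place of 187.5) gives about 25–98.

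**The case against.** The fair case against is that days on drug is a section 6.3 variable and not a primary or secondary endpoint. SAP 4.1 and 4.2 set no hypotheses or decision rules, SAP 8.2 calls the subgroup tests purely explorative, and few readers would be misled by leavers having fewer days. All of that limits the weight of the point. It does not save the test: section 4 gives hypothesis generation as its purpose, and a test that rejects whatever the truth cannot serve that purpose. The dose-sequence artefact is also much less obvious than the switched/remain one.

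Three stronger readings are tempting, and the documents do not support them.

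- *Every test in rows 26–27 is invalid.* Only one of the five subgroups is defined directly by staying on drug, and medication history is sound.
- *The responder comparisons are certain to reject.* SAP 1.1 keeps switched patients under observation and schedules EASI, IGA and SCORAD at every visit. If that is achieved, the rate is about 5%. The risk is real because visits are not mandatory and Protocol 10.3 makes follow-up after discontinuation depend on available documentation.
- *81–100% applies to the listed dose sequences.* That range is for a pooled contrast. SAP 5.4 lists separate classes, pooled only when small, and does not say how a two-group test is applied to six of them.

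**Conclusion.** The concern holds within these limits. The switched/remain test on days on abrocitinib is circular and should not be run. Changed-versus-constant dose contrasts are biased by about 28–82 days under the assumed rates, with false rejection anywhere from about one in five to certain, depending on class size, persistence and how often doses change. Changed-versus-changed contrasts and medication history keep their level, and the responder comparisons are at risk only under the conditions above. The switched/remain conclusion follows from the definitions. The other figures rest on assumed rates and a 5% level that the SAP does not set. No primary or secondary endpoint result is affected.

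A reader might infer that the Kaplan-Meier and Cox methods named in Protocol 9.7 would cure this. They would handle incomplete follow-up, but not classes formed from later information.

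**What to change.** 1. In SAP 8.2.3 rows 26–27, and in the closing sentence that sends all section 6.3 endpoints to all subgroups, remove the switched/remain comparison for days on abrocitinib. Editing the rows alone would let the test back in through that sentence.
2. For dose sequence and both responder subgroups, report days on abrocitinib descriptively without a test. Add a note that these classes, and row 27's most-often-applied dose stratum, are defined after baseline.
3. If a comparison is wanted, use a Month 3 landmark: fix the class on data up to that visit, include only patients still on drug, pool changed versus unchanged dose, and count only later time.
4. Keep the test for medication history and the overall FAS summary.

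The cost is SAP wording and minor programming before database lock, with no new data. Some exploratory p-values are lost. A landmark leaves out patients who stop before Month 3: 750 × (1 − S^(91/365)), or about 41 at 80% persistence and 119 at 50%. They remain in the overall summary. Dose changes after Month 3 would not define a class.
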